7.2 Assessment and Recording of Adverse Events

The study team may contact the participant when an adverse event has been reported to collect further information on the AE, if needed. The team will determine if the adverse event is serious, unanticipated, related to TENS treatment, and if any action needs to be taken, for example, discontinue TENS use, or if further reporting to regulatory authorities is necessary.

Pregnancy:

Pregnancy itself is not regarded as an AE. However, TENS is not recommended for use during pregnancy and the participant will be withdrawn from treatment and the outcome of all pregnancies that occur during paternal or maternal exposure to study device (spontaneous miscarriage, elective termination, normal birth or congenital abnormality) must be followed up and documented even after the participant has been withdrawn from treatment.

8 MANAGEMENT OF UNANTICIPATED PROBLEMS

Unanticipated problems will be defined as unexpected adverse clinical symptoms related to TENS or electrode use, or to specific unexpected non-TENS adverse events as identified in Section 7.1. These will be reported on the adverse event CRF and will be reviewed at each

DSMB meeting. If unanticipated AE are uncovered that occur in >5% of enrolled participants, the consent form will be modified, and the AE will be specifically queried on the AE CRF going forward. Participants who have completed the study will be notified of any newly recognized TENS-related AE.

9 STATISTICAL CONSIDERATIONS

9.1 General Design Issues

This will be a cluster randomized pragmatic trial. A stratified randomization procedure will be used to randomize clinics to either no-TENS or TENS added to standard of care (routine physical therapy). Sites will be stratified by health system and size of practice site. Half of the clinics will be randomized to standard of care only and half of the clinics will be randomized to TENS plus standard of care.

We hypothesize that using TENS in a PT setting is feasible and that FM patients using TENS will have reduced movement-evoked pain and other symptoms and are more likely to reach their therapeutic goals and reduce medication use.

9.2 Outcomes

9.2.1 Primary Outcome (including definition)

Reduction of movement-evoked pain measured by 11-point NRS for pain during the Sit and Stand Test (stand up and sit down five times) from baseline to 60 days will be used as the primary outcome variable. The severity of pain will be measured on a 0 to 10 scale at each time where 0 is no-pain and 10 is worst pain imaginable. The baseline measurement will occur at home before the first instance of the patient applying the TENS device (or no TENS for control group patients). The primary outcome variable will be obtained after using the TENS unit for 30 minutes during the Sit and Stand Test with NRS for pain (movement-evoked pain) at the 60-day time point. All outcomes will be collected by the participant at home during Research Homework.

Movement-evoked pain will be operationalized by having the participant perform a Sit and Stand Test (sit and stand five times) and rating their pain with an NRS. Movement-evoked pain during 5TSTS was measured in our previous randomized clinical trial, the FAST study, and the change in this measure was used to calculate the sample size for the current study.

9.2.2 Secondary Outcome(s)

Change in the resting pain score from baseline (pre-TENS) to 60 days (post-TENS session) will be used as a secondary outcome variable. The severity of pain will be measured on a 0 to 10 scale at each time where 0 is no-pain and 10 is worst pain imaginable. Other secondary outcomes include change in the following domains:

- Pain interference (BPI)
- FM disease activity (FIQR)

- Resting fatigue (NRS)
- Movement-evoked fatigue (NRS)
- Multidimensional assessment of fatigue (MAF)
- Rapid assessment of physical activity (RAPA)
- Patient global impression of change (PGIC)

An exploratory outcome of patient-specific function using the patient-specific functional scale (PSFS) will be evaluated. We will also collect additional HEAL-specified measures (see study visit schedule) and medications.

9.3 Sample Size and Accrual

The required sample size was calculated to assess the effect of TENS+PT versus PT alone on the primary outcome of change from baseline to day 60 visit in pain after PT using two-independent samples t-test with inflation factor of $[1+(m-1)*ICC]$ applied to account for average cluster size (m) and intra-cluster correlation (ICC). From the FAST study, there was a standard deviation of 2 units for change in movement-evoked pain during the five times sit to stand (5TSTS) Test. There was a greater decrease in pain with active-TENS compared to placebo-TENS of 1.3 (95% CI: 0.34, 2.2) for movement-evoked pain during 5TSTS. Compared to no-TENS, there was a greater decrease in pain with active-TENS of 1.8 (95% CI: 1.0, 2.8) for movement-evoked pain during 5TSTS. For this cluster randomized pragmatic trial comparing TENS+PT vs. PT alone, sample size was determined such that the statistical test at the 0.05 significance level will be able to detect a difference of at least 1.0 in mean change in pain with 80% power. Participants randomized to treatment arm will be clustered by clinic since clinics will be randomized for ease of implementation and thus, an estimate of the intra-cluster correlation (ICC) is needed for the sample size calculation. With no prior estimate of ICC, the required sample size per treatment arm (or participants per facility) for the desired detectable mean difference of 1.0, assuming SD=2.0, was calculated for combinations of ICC values and number of facilities per treatment arm; see Table 1 for ICC values for a sample size <600 participants per treatment arm. In a pilot study examining a non-pharmacological intervention for pain by our group we show an ICC of 0.01, DeBar and colleagues used an ICC of 0.002 for sample size calculation for a chronic pain population, and Adams et al. showed widely varying ICCs between data sets but the majority of patient-reported outcomes were below 0.095 ICC. Therefore, originally, we calculated the study sample size for ICC value between 0.12 and 0.14. We were conservatively estimating sample size of complete data from 456 participants total with 228 per treatment arm and 9 to 12 facilities per arm, which would allow an ICC of 0.12 to 0.14. The dropout rate in the previous randomized clinical trial from our group, in the FAST study, was 12% at 30 days follow-up. Since follow-up is 60 days in the proposed study, we expect a higher drop-out rate. The drop-out rate includes those patients who complete the informed consent form but do not complete the baseline assessment as a part of day 1 home activities, as well as those patients who start study and dropout prior to day 60. To account for up to 24% drop-out rate, a total of 600 participants (300 per arm) to be enrolled was originally planned. Table 4 shows the needed number of participants per facility (total participants within treatment arm), for specified ICCs throughout the range of 9 to 12 facilities per treatment arm (F), to detect a mean difference of at least 1 unit (NRS, 0-10) in pain at the 0.05 significance level with 80% power. Numbers in black show where we would be powered to detect a difference based on number of

facilities and different ICCs for n=300/arm while the tan numbers show ICCs for >300 per treatment arm.

For example, if the ICC is 0.14, to reach 80% power with 12 clinics in each arm, we need to have complete data from 19 patients per clinic, 228 patients in each arm: 456 patients total.

It should be noted that, we expect to enroll on average 25 patients per clinic for the scenario with 12 clinics per treatment arm. We expect some variability on the number of patients enrolled from each clinic.

Number of clinics will be increased in case the originally randomized clinics are not enrolling enough patients. In such scenario, the original overall sample size of 600 patients will be enrolled from more centers. Enrolling same number of subjects from more clinics gives higher statistical power compared to enrolling the same number of subjects from less number of clinics. Therefore, the scenario of adding more clinics would allow a higher drop-out rate from 600 enrolled patients. The randomization of new sites will be stratified based on health system and size of the practice site consistent with the original randomization. We will conduct an interim ICC recalculation after the first 200 participants have been enrolled (approximately 1/3 of the sample) for the purpose of determining ICC for the primary outcome measure. This analysis is to assess the primary outcome variable only for the purpose of calculating the ICC value and will not require unblinding of randomization. Therefore, it does not have an impact on the type I error rate and there is no change in our planned analysis on our statistical analysis plan. This analysis will only be used to determine the final number of subjects per site should be changed based on the ICC value. There are no stopping rules.

ICC	Table 1: ICC values by facilities (F) per treatment arm; subjects per site (total subjects)			
	F=9	F=10	F=11	F=12
0.050	11 (99)	9 (90)	8 (88)	7 (84)
0.100	23 (207)	16 (160)	13 (143)	11 (132)
0.110	30 (270)	20 (200)	15 (165)	12 (144)
0.120	43 (387)	25 (250)	17 (187)	14 (168)
0.125	56 (504)	28 (280)	19 (209)	14 (168)
0.130	--	34 (340)	21 (231)	16 (192)
0.135	--	41 (410)	24 (264)	17 (204)
0.140	--	53 (530)	27 (297)	19 (228)
0.145	--	--	32 (352)	21 (252)
0.150	--	--	39 (429)	23 (276)
0.155	--	--	51 (561)	26 (312)

The original sample size calculation conservatively assumed the ICC values to change between 0.12 and 0.14, subjects to be enrolled from 12 clinics in each group and approximately equal number of subjects to be enrolled from each clinic. During the conduct of the study, we recruited some clinics, and some other clinics were not actively enrolling. It was also observed that the number of patients enrolled per clinic was variable. Coefficient of variation (CV) is the ratio of standard deviation (sd) to the mean (CV = sd / mean), in terms of the enrollment per clinic. Due to variable enrollment numbers per clinic, we needed to account for variation in the number of enrolled participants per clinic by applying CV of subjects per clinic in the sample size calculation.

The number of active clinics at the time of the ICC recalculation was 28 where 26 clinics (13 in each treatment) had at least one participant with day 1 and day 60 assessments. The observed CV was 0.6.

We met with Drs. [name] and [name] from the NIH Collaboratory Biostatistics Core in November 2022 to discuss our sample size recalculation plan. They had two recommendations: 1) recalculating the ICC value based on the adjusted model, consistent with the final analyses. 2) Calculating the ICC and the Jackknife estimate of standard error (SE) of ICC, and calculating the sample size using both the current estimate of ICC and ICC + 1SE as a conservative estimate.

When the interim ICC recalculation was conducted to determine the current ICC value based on the adjusted model, consistent with the SAP, with ~228 enrolled subjects, the calculated ICC value was 0.05 with the Jackknife estimate of the SE of ICC is 0.07. Taking into account the variable sample size per clinic (CV = 0.6) and using 13 clinics/group, sample size was estimated at 450 enrolled subjects to obtain a final number of 342 participants completing day 60 based on a 24% drop out rate. This sample size provides >90% power for ICC = 0.05, and 81%

power for ICC = 0.10 and 78% power for ICC of 0.12 (ICC + 1SE = 0.05 + 0.07). The study sample was updated as 450 assuming ICC value of 0.10. The sample size recalculation was presented to NIAMS and the DSMB. Both NIAMS and the DSMB recommended approval of the change in sample size.

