2.2 Supporting Data

Our multi-institutional and multi-disciplinary research group recently completed an NIH/NIAMS funded(UM1 AR063381) randomized placebo-controlled clinical trial (N=301), FAST: Fibromyalgia Activity Study with TENS (NCT01888640), that showed Active-TENS (compared

to Placebo-TENS or No-TENS) reduced pain and fatigue during movement and at rest acutely (during the first application) and following 4 weeks of daily use. After the randomized phase, all groups received Active-TENS – there was sustained improvement in the Active-TENS group and equivalent improvement in the groups originally randomized to Placebo-TENS or No-TENS. Dramatic improvement in the global rating of change occurred for the Active-TENS group when compared to Placebo-TENS or No-TENS groups. TENS was well tolerated with <5% of participants reporting pain with TENS or irritation with the electrodes, which were the most common adverse events.

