5.5 Participant compliance

The TENS unit collects data on usage electronically. Participants will be expected to connect device to a phone application once per week when their data will be uploaded to a cloud. We will receive regular information on all units utilized from Quell. Usage will be assessed in terms of number of 60-minute sessions and total number of minutes. In our previous study the total number of minutes was used for the per protocol analysis. As the current study will be based on intention to treat, usage information will also be used primarily for the per protocol analysis.

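### The planning SD of 2.0 is in tension with the FAST confidence intervals quoted beside it, and the recalculated power depends on it with almost no margin

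*Protocol*

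**What the plan says.** Protocol 9.3 sizes the trial for a 1.0-point difference in mean change in pain, with 80% power at the 0.05 level. Its variability input is FAST, where "there was a standard deviation of 2 units for change in movement-evoked pain during the five times sit to stand" test. The next sentences give the FAST effects: "There was a greater decrease in pain with active-TENS compared to placebo-TENS of 1.3 (95% CI: 0.34, 2.2") and, against no-TENS, a "greater decrease in pain with active-TENS of 1.8 (95% CI: 1.0, 2.8"). The required numbers were then worked out "assuming SD=2.0, was calculated for combinations of ICC values and number of facilities per treatment arm". SAP 9 repeats the same SD and intervals.

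Protocol 2.2 describes FAST as a "randomized placebo-controlled clinical trial (N=301") with Active-TENS, Placebo-TENS and No-TENS groups. Protocol 9.3 adds: "The dropout rate in the previous randomized clinical trial from our group, in the FAST study, was 12% at 30 days follow-up".

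The interim recalculation, described in both documents, reports an ICC of 0.05 (jackknife SE 0.07) from the adjusted model and a cluster-size CV of 0.6. It reports no SD. With 13 clinics per arm, 450 enrolled and 342 completers, it states power above 90% at ICC 0.05, 81% at 0.10 and 78% at 0.12. The target of 450 was adopted on ICC 0.10.

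**The concern.** An SD of change and a confidence interval for a difference in mean change, taken from the same trial, are linked by the number analysed per arm. With roughly 100 per arm, an SD of 2 should give intervals clearly narrower than those quoted. Neither document gives FAST's per-arm numbers, analysis set, interval method or time point, or says whether the 2 is a raw or a residual SD. The two figures therefore cannot be reconciled from the text.

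What is at stake is the power statement behind the current sample size. The recalculation re-estimated ICC and CV and left the SD alone. If the SD that applies to the baseline-adjusted primary analysis exceeds 2.0, the stated chance of detecting a 1.0-point difference is too favourable.

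**Working it through.** **Inputs from the documents.** Difference 1.0; SD 2.0; two-sided 0.05; 13 clinics per arm; 342 completers (171 per arm, mean m = 342/26 = 13.15 per clinic); CV 0.6; FAST intervals and N = 301. **Assumed.** Roughly equal FAST arms, with 100 analysed per arm, or 88 after 12% dropout; the FAST interval method; the design-effect formula for unequal clinics and its degrees of freedom.

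**1. The plan's own figures.** A t-test with difference 1.0 and SD 2.0 needs 64 per arm. Patients per clinic are 64(1 − ICC)/(F − 64·ICC), rounded up. At ICC 0.14 and F = 12 this is 55.04/3.04 = 18.1, so 19 per clinic and 228 per arm, as stated. All cells of Protocol Table 1 reproduce this way, and 342/0.76 = 450.

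For the recalculation, take design effect = [1 + (m − 1)ICC]/RE, with RE = 1 − CV²·λ(1 − λ) and λ = m·ICC/[1 + (m − 1)ICC]. At ICC 0.10, λ = 1.315/2.215 = 0.594, RE = 0.913, design effect = 2.43 and effective n = 171/2.43 = 70.5 per arm. The SE is 2.0·√(2/70.5) = 0.337. A noncentral t on 24 df gives 81.3%. At ICC 0.05 and 0.12 the results are 91.6% and 77.3%. The stated figures (above 90%, 81%, 78%) are matched within a point, so they appear to rest on SD 2.0.

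**2. SD implied by the FAST intervals.** SD = half-width/z ÷ √(2/n). Half-widths are (2.2 − 0.34)/2 = 0.93 and (2.8 − 1.0)/2 = 0.90. The second interval is uneven about 1.8, so its shorter side, 0.8, is shown as well. Each range runs from n = 88 to n = 100.

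| Interval method | z | 0.93 | 0.90 | 0.80 (shorter side) | n per arm at which SD = 2.0 (0.93 / 0.90 / 0.80) |
|---|---|---|---|---|---|
| Ordinary | 1.960 | 3.15–3.36 | 3.05–3.25 | 2.71–2.89 | 36 / 38 / 48 |
| Bonferroni, 3 | 2.394 | 2.58–2.75 | 2.49–2.66 | 2.22–2.36 | 53 / 57 / 72 |
| Bonferroni, 6 | 2.638 | 2.34–2.49 | 2.26–2.41 | 2.01–2.14 | 64 / 69 / 87 |

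**3. Margin on the SD.** With the formula of step 1, the largest SD keeping 80% power is 2.39, 2.03 and 1.93 at ICC 0.05, 0.10 and 0.12. The documents do not name the formula. Three design-effect versions (the one above; 1 + [(CV² + 1)m − 1]ICC; and the same with CV² multiplied by 12/13) were each combined with z, individual df and 24 df. Over these nine, the limit is 1.93 to 2.12 at ICC 0.10 and 2.33 to 2.49 at ICC 0.05.

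**4. Power and detectable difference if the applicable SD is larger** (formula of step 1):

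| SD | Power for 1.0 at ICC 0.05 / 0.10 / 0.12 | Difference detectable with 80% power |
|---|---|---|
| 2.0 | 92% / 81% / 77% | 0.84 / 0.98 / 1.03 |
| 2.5 | 76% / 63% / 58% | 1.05 / 1.23 / 1.29 |
| 3.0 | 61% / 48% / 44% | 1.26 / 1.48 / 1.55 |

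**5. Effect of baseline adjustment.** If the FAST intervals are for raw change and variances are equal at both times, adjusting for baseline multiplies the SD by √((1 + r)/2), where r is the correlation of baseline with Day 60 pain. No r is given. At ICC 0.10, a raw SD of 2.5 keeps 81% if r is at most 0.28 and gives 75% at r = 0.5. A raw SD of 2.75 keeps 80% only if r is at most 0.09. A raw SD of 3.05 gives 75% at r = 0 and less for any higher r. At ICC 0.05, 80% is kept for r up to 0.82, 0.50 and 0.22 respectively.

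**6. Would the previous size settle it?** With 456 completers in the same 26 clinics, the 80% limit at ICC 0.10 rises only from 2.03 to 2.15, and SD 2.5 would give 67%.

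**The case against.** The case for leaving SD 2.0 alone is substantial. The back-calculation depends on FAST details that neither document gives. A smaller analysed set would explain the gap, and Protocol 5.5 shows that one may have existed: "In our previous study the total number of minutes was used for the per protocol analysis". A heavily widened interval would also explain it: with six comparisons, 88 per arm and the shorter side of the second interval, the implied SD is 2.01. The assumption of 2.0 is disclosed and the arithmetic that follows from it is correct. The primary model in SAP 7.2 adjusts for baseline pain, so a raw SD of change is not the relevant one; if 2.0 is raw and correct, the stated power is if anything conservative. The plan sized on twice the observed ICC. Both FAST effects exceed 1.0: at ICC 0.10, unadjusted, power over SD 2.5 to 3.36 is 84% to 60% for an effect of 1.3 and 98% to 86% for 1.8. The recalculation plan was discussed with outside statisticians, and NIAMS and the DSMB recommended approval of the new size.

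Most of this stands, and it rules out two stronger readings. A reader might infer that FAST shows SD 2.0 to be wrong and the trial to be underpowered. The documents do not support that, because the per-arm n, interval method and r are all missing. A reader might also infer that the cut to 450 created the problem. It did not: the SD was carried over unchanged, and the larger size would have had nearly the same sensitivity to it.

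What the objection does not supply is a reconciliation. Each favourable explanation needs a fact about FAST that the plan does not state.

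**Conclusion.** The point holds as a tension between the plan's SD and the plan's own source. Under roughly equal FAST arms with 88 to 100 analysed, the half-widths imply an SD from about 2.3 to 3.4, depending on the interval method. SD 2.0 needs a smaller analysed set or a heavily widened interval, and neither is stated. This is a weakness of the initial planning input that the recalculation inherited.

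The 81% at ICC 0.10 needs an applicable SD of about 2.0, and 80% is lost somewhere between 1.93 and 2.12 depending on the formula. At the observed ICC of 0.05 there is more room, to about 2.4. At SD 2.5, power for the 1.0 target would be about 63% and 76% respectively; baseline adjustment could recover some or all of that loss. Only the power statement is affected. The treatment estimate and type I error are not, and SAP 7.2 already treats non-rejection as insufficient evidence. Worth fixing; confidence is medium, because the FAST details are assumptions.

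**What to change.** Compute the total SD (clinic plus residual variance) from the adjusted model already fitted for the interim ICC, blind to arm. The residual SD alone would flatter the result: at ICC 0.10 and total SD 2.0 it is 2.0·√0.9 = 1.90, which would give 85%. State whether the treatment term was in that model. If it was not, correct for the assumed difference d by subtracting d²/4 from the variance; a true SD of 2.0 appears as about 2.06 with d = 1.0 and 2.19 with d = 1.8.

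In Protocol 9.3 and SAP 9:
- restate power and the difference detectable with 80% power at ICC 0.05, 0.10 and 0.12, using that SD or a range such as 2.0 to 3.0;
- name the design-effect formula and degrees of freedom;
- say how SD 2.0 relates to the quoted FAST intervals: per-arm n, analysis set, time point, interval method, and raw or residual SD.

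The cost is one calculation on data already held and new wording in two sections. It slightly widens the stated ICC-only purpose of the interim look, which should be acknowledged, but needs no unblinding. Enrolment, endpoint and primary analysis do not change. The downside is that the stated power may become less favourable.

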9.4 Data Analyses

Descriptive statistics (means, medians, percentages, standard deviations, and interquartile ranges) will be computed for demographic and baseline variables for each of the treatment groups. The distributions of continuous variables will be evaluated for normality. If data are not normally distributed, appropriate transformation will be applied, or non-parametric methods will be used. Demographic and baseline variables will be compared between treatment groups using two independent samples t-test for continuous variables, Wilcoxon-rank sum test for ordinal as well as non-normally distributed continuous variables, and Pearson Chi-square test for categorical variables. Variables that are found to significantly differ between the groups may be used as possible covariates in the comparison of outcome measures between the treatment groups.

Intent-to-treat (ITT) analyses will be conducted that will include all participants that have been randomized.

The primary endpoint to assess efficacy of TENS+PT compared to PT alone is change in movement-evoked pain during the Sit and Stand Test from baseline to 60 days. This will be tested using linear mixed model analysis for repeated measures with treatment group, time, and treatment*time interaction as fixed effects. Random effects include facilities (within treatment), and participants (within facility, within treatment). In fitting the mixed model, appropriate covariance structures for longitudinal measures within participant will be considered. Our initial approach will be to assess compound symmetry and heterogeneous compound symmetry covariance structures. However, we will also explore different covariance structures and will not only be limited to these two options. These decisions will be finalized during the UG3 phase of the proposed study. The final covariance structure will be selected based on Akaike Information Criteria (AIC) and Schwarz's Bayesian Information Criteria (BIC). From the fitted model, differences in mean change between treatment groups will be assessed by test for treatment*time interaction effect. It is expected that stratified randomization will lessen the need for covariate-adjusted analyses. However, in the event that adjusted analyses are necessary, a secondary comparison of the primary endpoint between groups will be made by expanding the linear mixed model to include covariates. Potential covariates include age, race, ethnicity, TENS dose/intensity, opioid use, and use of FM (for example, anti-depressants, α 2-delta ligands) medications. In addition, opioid use at baseline as a possible effect moderator of TENS will be examined by including an opioid*treatment*time interaction in the model. If found to be significant, then secondary analyses to test for TENS efficacy by opioid status will be performed with p-values adjusted using Bonferroni's method for multiple comparisons. Statistical significance for efficacy of TENS+PT vs. PT alone will be based on a two-tailed test at the 0.05 significance level with treatment effect summarized as mean difference with 95% confidence interval. Similar analyses will be performed for secondary outcome measures.

In the case of subject drop-out, reasons for subject drop-out will be recorded and compared between treatment groups. Subject characteristics and outcome measures collected prior to drop-out for those that drop-out will be compared to those that complete the study. In the presence of missing data, under the assumption of missing at random (MAR), linear mixed model analysis, which can handle incompletely observed subjects and uses a likelihood estimation method, will provide correct likelihoods and lead to valid estimates. However, since the data under analysis cannot distinguish if data is MAR or it is missing not at random (MNAR), sensitivity analysis will also be performed. Methods for sensitivity analysis such as marginal delta adjustment, conditional delta adjustment, reference-based controlled imputation, and other

pattern mixture models will be considered. If needed, variables will be transformed to satisfy approximate normality before imputation and retransformed back to original scale. To avoid imputation bias, all variables in the substantive analyses and, if feasible, other variables in the study database predictive of the missing values or influencing the cause of missing data will be included. Multiple imputation analyses using SAS PROC MI and SAS PROC MIANALYZE will be conducted. Any differences in results of the primary analysis and the sensitivity analyses, and possible reasons will be reported.

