### 7.4 Covariate Adjustments

It is expected that stratified randomization will lessen the need for covariate-adjusted analyses. However, in the event that adjusted analyses are necessary, a secondary comparison of the primary endpoint between groups will be made by expanding the linear mixed model to include covariates. Potential covariates include age, race, ethnicity, TENS dose/intensity, opioid use, and use of FM medications (for example, anti-depressants,  $\alpha_2$ -delta ligands). In addition, opioid use at baseline as a possible effect moderator of TENS will be examined by including an opioid\*treatment interaction in the model. If found to be significant, then secondary analyses to test for TENS effectiveness by opioid status will be performed with p-values adjusted using Bonferroni's method for multiple comparisons. Statistical significance for effectiveness of TENS+PT vs. PT alone will be based on a two-tailed test at the 0.05 significance level with treatment effect summarized as mean difference with 95% confidence interval.

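### Protocol 9.4 tests baseline balance as if patients, not clinics, had been randomised, and lets the resulting p-values nominate covariates for the adjusted comparison

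*Protocol*

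**What the plan says.** Protocol 9.1 randomises clinics, half to each arm, stratified by health system and practice size. Protocol 9.4 then sets out the baseline comparison: "Demographic and baseline variables will be compared between treatment groups using two independent samples t-test for continuous variables", with "Wilcoxon-rank sum test for ordinal as well as non-normally distributed continuous variables" and "Pearson Chi-square test for categorical variables". None of these has a clinic term, and no significance level is stated for them. The next sentence makes the results a route to adjustment: "Variables that are found to significantly differ between the groups may be used as possible covariates" when outcomes are compared.

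Both Protocol 9.4 and SAP 7.4 describe a covariate-adjusted version of the primary comparison. It is secondary and is run only "in the event that adjusted analyses are necessary". Both list potential covariates: three demographic items, opioid use, fibromyalgia medication and TENS dose or intensity. Neither says what makes adjustment necessary.

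The SAP differs from the protocol on baseline data. SAP section 5 tabulates baseline variables by arm and names no test. SAP 7.2 fixes the primary model: treatment, baseline movement-evoked pain, clinic size and a random clinic effect.

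**The concern.** The plan treats patients in a clinic as correlated in its sample size and outcome models, but as independent at baseline. An individual-level test understates the variance of the difference between arms when whole clinics are allocated, so it declares chance imbalance too often. A reader of the baseline table could wrongly conclude that randomisation failed or that recruitment was biased.

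The selection rule has a second weakness that does not depend on the ICC. A covariate helps when it predicts the outcome. Whether it happens to differ significantly between arms is a separate matter, so the rule can leave out a prognostic variable and let in an irrelevant one, after the data are seen. At stake are the printed baseline p-values, and the precision and prespecification of the secondary adjusted comparison. SAP section 8 applies the section 7 methods to the secondary outcomes, so the same looseness carries over to them.

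**Working it through.** **Inputs from the documents** (Protocol 9.3, SAP 9): 13 clinics per arm; 450 enrolled; 24% drop-out, leaving 342 at day 60; cluster-size CV 0.6; difference 1.0; SD 2.0; interim ICC 0.05 (SE 0.07) for change in pain. The drop-out figure includes patients who never complete the day 1 baseline, so the number with baseline data lies between 342 and 450.

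**Assumptions.** The baseline tests use 0.05 two-sided, the level stated for efficacy. Baseline ICCs are not given. The range 0.002 to 0.10 is used because these values appear in Protocol 9.3 in connection with pain outcomes.

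**The plan's own figures reproduce.**
- Drop-out: 342/(1 − 0.24) = 450.
- Design before recalculation: the t-test needs 64 per arm. With 12 clinics per arm and ICC 0.14, patients per clinic = 64 × (1 − 0.14)/(12 − 64 × 0.14) = 55.04/3.04 = 18.1. This rounds up to 19, or 228 per arm, as stated.
- Updated power: m = 342/26 = 13.15; λ = m·ICC/[1 + (m − 1)ICC]; relative efficiency RE = 1 − CV²·λ(1 − λ); design effect [1 + (m − 1)ICC]/RE; non-central t on 24 df. This gives 91.6%, 81.3% and 77.3% at ICC 0.05, 0.10 and 0.12, against the stated >90%, 81% and 78%.

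**False-flag rate of an unclustered baseline t-test.** The naive test weights patients equally, so the design effect is DE = 1 + [(1 + CV²)m − 1]·ICC. The true rejection rate is 2[1 − Φ(1.96/√DE)].

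Worked case, 450 patients, ICC 0.05: m = 450/26 = 17.31; DE = 1 + (1.36 × 17.31 − 1) × 0.05 = 2.127; 1.96/√2.127 = 1.344; rate 17.9%.

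| Assumed ICC | DE, N = 342 | Rate | DE, N = 450 | Rate |
|---|---|---|---|---|
| 0.002 | 1.034 | 5.4% | 1.045 | 5.5% |
| 0.01 | 1.169 | 7.0% | 1.225 | 7.7% |
| 0.05 | 1.844 | 14.9% | 2.127 | 17.9% |
| 0.10 | 2.689 | 23.2% | 3.254 | 27.7% |

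**Simulation check** (26 clinics, CV 0.6, 450 patients, 4,000 runs per setting). At ICC 0.05 the t, rank-sum and chi-square tests reject 17.3%, 17.0% and 13.4% of the time. At ICC 0.10 they reject 28.2%, 27.2% and 21.6%. Across all settings run, a t-test on clinic means rejects 4.6% to 5.3%.

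**Several variables at once.** SAP section 5 lists eight baseline variables. Suppose all were tested and were independent. The nominal chance of at least one false flag is 1 − 0.95⁸ = 34%. Simulated t-test rates at 400 patients (15.6% at ICC 0.05, 24.9% at 0.10) give 1 − 0.844⁸ = 74% and 1 − 0.751⁸ = 90%. Using the lower chi-square rate for the five variables treated as categorical, with the rates at 450 patients, gives 1 − 0.827³ × 0.866⁵ = 72% and 1 − 0.718³ × 0.784⁵ = 89%. At ICC 0.01 the t-test rate gives 1 − 0.923⁸ = 47%. All of these rest on assumed ICCs and on independence.

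**The case against.** Much of the case on the other side stands.

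- **Permissive wording.** A reader might infer that significant variables automatically enter the model, or that chance imbalance determines the adjusted result. The text does not support this: it says *may* and *possible*, and candidate covariates are named beforehand without reference to baseline p-values.
- **Primary result.** SAP 7.2 fixes the primary model, and baseline pain is in it whatever the imbalance.
- **SAP already tabulates only.** The testing rule sits in the protocol alone.
- **Error rate.** A reader might also infer that the adjusted treatment test has an uncontrolled type I error. Nothing in the documents shows that. A simulation applied the rule mechanically (342 patients, 26 clinics, CV 0.6, eight candidates, clinic random-effect model, 3,000 runs per setting) and gave 3.1% to 4.8%.
- **Size.** The ICC of 0.05 belongs to change in pain, and Protocol 9.3 also cites 0.002 and 0.01, where inflation is small. Stratification helps too. If half the between-clinic variance lay between six health systems (an assumption), the simulated rate would fall from 15.5% to 11.4% at ICC 0.05 and from 25% to 17% at 0.10.

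Three things survive. A list of potential covariates is not a fixed set: items can be dropped, Protocol 9.4 can add others, and TENS dose is measured after randomisation. The significance rule is the only data-based criterion either document offers for adjusting. And in the same simulation with prognostic covariates, p-value selection gave a treatment-estimate SD of 0.157, 0.154 and 0.191 in three settings (arbitrary units). That is better than no adjustment (0.166, 0.168, 0.224) but worse than entering all eight in advance (0.146, 0.144, 0.171).

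**Conclusion.** The point holds in limited form. Followed as written, Protocol 9.4 produces baseline p-values that are too small for a clinic-randomised trial. The true level of a nominal 5% t-test is about 15-18% if a baseline variable has ICC 0.05 and 23-28% at 0.10, but close to nominal at 0.002. These rates rest on assumed ICCs, 26 clinics and CV 0.6, and do not allow for stratification.

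The objection to choosing covariates by significance of imbalance holds at any ICC, and the undefined trigger for adjustment leaves that choice open until the data are seen. The consequence is confined to the reported baseline p-values and to the precision and prespecification of secondary analyses. The SAP primary test is sound on this point. The matter is worth correcting because it is cheap to put right, not because it threatens the main conclusion.

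**What to change.** In Protocol 9.4, delete the baseline significance tests and the sentence that draws covariates from them. Present baseline summaries by arm without p-values, which brings the protocol into line with SAP section 5.

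In SAP 7.4, replace the conditional wording with a fixed covariate set for the secondary adjusted model. Choose it now on prognostic grounds from baseline variables already collected (for example age, FIQR score and baseline opioid use), and fit that model whatever the observed imbalance. Leave TENS dose or intensity out of this set, because it is not a baseline variable. Make the matching change to the adjusted-analysis text in Protocol 9.4.

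If the sponsor wants to keep baseline tests, for instance to look for differential recruitment after clinics were allocated, they should account for clinic, such as a t-test on clinic means or a model with a random clinic effect.

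The cost is wording in two sections and the usual review of a protocol amendment. No new data are needed, and there is less analysis to run.
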